7.3 Lost to follow-up

A patient will be considered lost to follow-up if they repeatedly fail to return for scheduled visits and is unable to be contacted by the trial site.

The following actions must be taken if a patient fails to return to the clinic for a required trial visit:

- The site must attempt to contact the patient and reschedule the missed visit as soon as possible and counsel the patient on the importance of maintaining the assigned visit schedule and ascertain whether or not the patient wishes to and/or should continue in the trial.
- Before a patient is deemed lost to follow-up, the investigator or designee must make every effort to regain contact with the patient (where possible, three telephone calls and, if necessary, a certified letter to the patient's last known mailing address or local equivalent methods). These contact attempts should be documented in the patient's medical record.
- Should the patient continue to be unreachable, they will be considered to have withdrawn from the trial.

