1.3 Schedule of activities

The schedule of activities (SoA) and procedures for Phase I (mFOLFIRINOX + BNT321) is shown in Table 1 and for Phase II (mFOLFIRINOX ± BNT321) is shown in Table 2 and Table 4.

Assessments should be performed before trial treatment administration (on the applicable days) or any planned intervention, with the exception of post-dose blood sampling for exploratory PD, PK, immunogenicity assessments and any samples required for supplementary R&D. For the primary DFS endpoint, which includes disease assessment by computed tomography (CT)/magnetic resonance imaging (MRI) and serum CA19-9, analyses must be performed at screening (baseline post-operative scans <4 weeks and CA19-9 within 3 weeks of Cycle 1 Day 1 are required). After Cycle 1 Day 1 scans and CA19-9 must be performed every 3 months (12 weeks) for 2 years, and then every 6 months for 3 years thereafter (±7 days). Patients should be evaluated with the same imaging and assessment method (CT or MRI) throughout the trial.

Investigators must make every effort to adhere to the given visit schedule and to perform all assessments within the given time for each visit as specified in the SoA tables. This is especially true for the PK assessments according to the SoA in Table 3. Lost to follow-ups should be avoided and every effort should be taken by the trial site to follow-up on the whereabouts of the patients and their survival status.

Page 10 of 127 Version: 2.0 Date: 22 JAN 2024

Table 1: Schedule of activities and procedures – Phase I (mFOLFIRINOX + BNT321)

Treatment cycle (14 d)	SCR 2	Сус	ile 1	1 Cycle 2 Cycle 3 Cycle 4-12				2	BNT321 monotherapy Cycles 13-24 ³	EOT4	Safety FU ⁵	Survival FU ⁶				
Days 1		1	8	1	3	8	1	3	8	1	3	8	1			
Informed consent 7	Х															
Eligibility	X															
Medical history 8	Х															
TB screening ⁹	X															
DPD deficiency screening ¹⁰	Х															
UGT1A1 mutation screening 11	Х															
Demographics	Х															
Height	Х															
Weight ¹²	Х	Х		Х			Х			Х			Х	Х		
Physical examination	Х													X		
Symptom-directed exam 13		X	[X]	Х	[X]	[X]	Х	[X]	[X]	Х	[X]	[X]	Х			
Vital signs ¹⁴	Х	Х	Х	Х	X	Х	Х	X	Х	Х	Х	Х	Х	X	X	
Performance status 15	Х	Х	Х	Х	X	Х	Х	X	Х	Х	Х	Х	Х			
HRQoL 16	Х						Х			[X]			[X]	X		X
Concomitant medications 17	Х	Х	Х	Х	X	Х	Х	Х	Х	X	Х	Х	Х	X	Х	
Adverse events 18		X	Х	Х	X	Х	Х	X	Х	X	Х	Х	Х	X	Х	
ECGs 19	Х	Х		Х			Х			[X]			Х	Х		
Hematology ²⁰	X	Х	X	Х		Χ	X		X	X		X	Х	X	X	

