- 5. Safety FU visit is performed 28 days (±14 days) after last dose of BNT321. EOT and safety FU visits may be combined for patients who discontinue BNT321 outside of a clinic visit or who had no Grade 2 or higher toxicity at their last trial visit.
- 6. Survival FU visits will be performed beginning 12 weeks (±30 days) after safety FU until 5 years after C1D1. DFS status will be recorded every 3 months for 2 years and then every 6 months for the next 3 years. All patients will be contacted, or the medical records reviewed to report survival status, disease progression and to provide an update on CA 19-9 and tumor imaging. Initiation of any additional therapy for pancreatic cancer will be documented.
- 7. Informed consent will be obtained prior to performing any trial-specific screening procedures.
- 8. Medical history should include but not limited to lifetime history of cancer, tumor characteristics such as mutation status, cancer-related somatic genomic alterations and germline status, prior non-cancer significant medical conditions for the 2 years prior to trial entry, other clinically relevant diseases, including tuberculosis, surgeries, use of alcohol and/or drugs abuse and reproductive status.
- 9. For patients whom the treating physician considers to be at increased risk for infection, in which case testing should be done according to institutional practice standards at screening.
- 10. DPD testing to be done at screening if required by local regulations.
- 11. UGT1A1 testing at screening if required by local regulations.
- 12. Obtained at screening. Day 1 of every cycle and EOT, may be reduced to every other cycle based on investigator's discretion.
- 13. Symptom-directed physical examinations will be performed on Day 1 of each cycle prior to treatment administration and at any visit where the patient indicates new symptoms that require evaluation or based on investigator's discretion.
- 14. Vital signs e.g., blood pressure, body temperature, heart rate, and respiratory rate will be recorded on each designated visit days and prior to and approximately every 30 minutes until at least 2 h after completion of BNT321 infusion. On mFOLFIRINOX treatment visits, vital signs will be performed prior to start of infusion. On nontreatment visits, vital signs will be performed once. Vital signs will also be performed at the safety FU visit.

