7.2 Patient discontinuation/withdrawal from the trial

A patient who has consented during any phase of the trial, who requests to discontinue receipt of trial treatment, will remain in the trial, and the patient must continue to be followed for protocol specified follow-up procedures. The only exception to this is when a patient specifically withdraws consent for further continuation in the trial.

A patient will be withdrawn from the trial at any time at their own request or discontinued from the trial at any time at the discretion of the investigator for safety, behavioral, compliance, or administrative reasons.

Reasons for patient discontinuation from the trial include the following:

- Lost to follow-up;
- Death;
- Withdrawal of content;
- Patient noncompliance;

Page 71 of 127 Version: 2.0 Date: 22 JAN 2024

- Investigator decision;
- Trial terminated (closure of all sites) by sponsor;
- Protocol deviation;
- Pregnancy.

See the SoA (Section 1.3) for data to be collected at the time of withdrawal/discontinuation from the trial and for any follow-up / further evaluations that need to be completed.

If discontinued from the trial, the patient will be permanently discontinued both from the trial and from the trial treatment at that time. In these cases, the sponsor will retain and continue to use any data collected before the permanent discontinuation.

If a patient withdraws from the trial, they may request destruction of any samples taken and not tested, and the investigator must document this in the site trial records.

Lack of completion of all or any of the withdrawal/early termination procedures will not be viewed as a protocol deviation as long as the patient's safety was preserved.

For guidance on premature termination or suspension of the whole trial, see Section 10.1.9.

Re-enrollment is not permitted following trial discontinuation.

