8.2.4 Survival follow-up

Following the safety follow-up visit, site staff will contact the patient every 3 months for 2 years and then every 6 months for the next 3 years or until the patient is lost to follow-up or dies. Survival follow-up will determine survival status and record if patients have taken any new anticancer treatments. This contact may be by telephone, E-Mail or other form of communication but must be documented in the source notes.

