9.3 Sample size determination

The sample size calculation is based on the primary endpoint of mDFS, ensuring that DFS will be adequately powered. The calculation of the required number of events is based on the following specifications:

- 1:1 randomization
- Hazard ratio (HR) = 0.60
- Significance level of α = 5% (two-sided)
- Power of 1- β = 90%

Based on these specifications CC (Section 9.2) at least 164 aggregate events (i.e. 55% maturity) in both arms will be required to demonstrate efficacy assuming a true effect size of HR = 0.60 with a power of 90% using a two-sided statistical test at 5% significance level.

The calculation of the required number of patients is based on the following assumptions:

- Median DFS time from randomization of 21.6 months in the mFOLFIRINOX group and 36 months in the combination group (assume HR = 0.60)
- Accrual duration: ~24 months for Phase I and Phase II
- Follow-up duration: until DFS event
- Drop-out rate: 10% per year

Based on these assumptions at least 300 patients in both arms combined will be required to observe the required number of DFS events (164) ~34 months after last patient in (LPI) (randomized).

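### Section 7.3 treats unreachable patients as withdrawn and Section 8.2.4 ends survival contacts at loss to follow-up, while Sections 1.3 and 4.1 keep contact or record review open to 5 years

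*Combined protocol and SAP*

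**What the plan says.** Some sections let follow-up stop when contact is lost.

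- Section 7.3 asks for a search first ("where possible, three telephone calls and, if necessary, a certified letter", or local equivalents). It then rules: "Should the patient continue to be unreachable, they will be considered to have withdrawn from the trial".
- Section 8.2.4 runs the survival contacts "for the next 3 years or until the patient is lost to follow-up or dies".
- Section 7.2 names loss to follow-up among the reasons for discontinuation from the trial. For patients so discontinued it adds that "the sponsor will retain and continue to use any data collected before the permanent discontinuation". It does not mention information that becomes available later.

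Other current text keeps follow-up open.

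- The introduction to Section 1.3 says that "every effort should be taken by the trial site to follow-up on the whereabouts of the patients and their survival status".
- Footnote 6 of Tables 1 and 2 and footnote 5 of Table 4 say: "All patients will be contacted, or the medical records reviewed to report survival status, disease progression".
- The synopsis (Section 1.1) and Section 4.1 collect survival information on all patients, with medical records as a named source, about every 12 weeks to 5 years. The only limits given are withdrawn consent and termination by the sponsor.
- Section 4.3 lists loss to follow-up and withdrawn consent as separate conditions.

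For planning, Section 9.3 assumes "Drop-out rate: 10% per year", with no definition and no split by reason. Section 9.5.3 censors OS for lost patients when they were last known to be alive.

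**The concern.** Being out of reach is not a decision by the patient, and consent still stands. Once the patient is labelled withdrawn, a site that reads 7.3 with 7.2 and 8.2.4 can reasonably conclude that its duty to look has ended. Record review is the one route in the plan that needs no contact with the patient, and this is the route put in doubt.

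Death from any cause is an event in DFS, RFS and OS. If some patients become unreachable because they have relapsed or are dying, censoring them at last contact is informative and the Kaplan-Meier and Cox estimates inherit the bias. The documents do not show that this happens, but the plan should not leave it to chance when records could settle vital status. A search not made during the trial may be impossible to make afterwards.

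**Working it through.** **1. The sections side by side.** Take a patient in year 2, off treatment, who has not answered calls or a letter and has not withdrawn consent.

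| Question | Sections 7.3, 7.2 list, 8.2.4 | Sections 1.1, 1.3, 4.1 |
|---|---|---|
| Status | Withdrawn / discontinued | Still within all patients |
| Survival contacts | End at loss | To 5 years |
| Record review for death or progression | Not mentioned | Allowed for every patient |
| What ends it for the individual | Loss of contact | Withdrawal of consent |

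Both columns are current text, and no section says which governs.

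**2. The plan's own figure.** Inputs from Section 9.3: HR 0.60, two-sided 5%, power 90%, 1:1 allocation.

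- Schoenfeld events = 4(1.960 + 1.282)² / (ln 0.60)² = 42.03 / 0.2609 = 161.1, so 162.
- Power at 164 events = Φ(√164 / 2 × 0.5108 − 1.960) = Φ(1.311) = 90.5%.

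The stated 164 is reproduced closely. Section 9.2 is redacted and may account for the two extra events.

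**3. How many patients drop out before a DFS event.** Inputs from Section 9.3: medians of 21.6 and 36 months, 300 patients (150 per arm), drop-out 10% per year. Assumptions: exponential times, uniform accrual, the same drop-out rate in both arms, and Phase II accrual A = 12 months. Section 9.3 gives only about 24 months for both phases together.

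- Event hazards per month: ln 2 / 21.6 = 0.03209 (control) and ln 2 / 36 = 0.01925 (combination).
- Drop-out hazard: η = −ln(0.9) / 12 = 0.00878.
- With κ = λ + η and F months from last patient in to the cut, the chance of dropping out first is (η/κ) × (1 − m), where m = [exp(−κF) − exp(−κ(F + A))] / (κA). For a DFS event, replace η/κ with λ/κ.
- 164 events are reached at F = 34.1, matching the plan's roughly 34 months.
- Control: κ = 0.04087, m = 0.1964. Drop-outs 150 × 0.2148 × 0.8036 = 25.9. Events 150 × 0.7852 × 0.8036 = 94.6.
- Combination: κ = 0.02803, m = 0.3268. Drop-outs 150 × 0.3132 × 0.6732 = 31.6. Events 150 × 0.6868 × 0.6732 = 69.4.
- Total: 164.0 events and 57.5 drop-outs (57.5 / 300 = 19%).

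The higher count in the combination arm comes only from its lower event hazard, since both arms have the same assumed drop-out rate. With accrual of 18 or 24 months, 164 events come at 31.3 or 28.7 months after last patient in and drop-outs stay at 57.5. Reading 10% per year as a rate of 0.10 gives 54.6.

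**4. What better tracing could do (illustration).** If effective loss fell to 5% per year, an assumed figure, 164 events would come about 29 rather than 34 months after last patient in. At 34 months about 176 events would be seen instead of 164.

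**The case against.** Several points on the other side stand.

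- Section 7.3 does not forbid record review or say that the search ends. That is inferred by reading it with 7.2 and 8.2.4, and Sections 1.3 and 4.1 already contain much of the repair.
- A reader might take the 7.2 sentence "The only exception to this is when a patient specifically withdraws consent for further continuation in the trial" as a general rule that only withdrawn consent ends follow-up. In context it concerns patients who ask to stop trial treatment, and the same section then lists further reasons for leaving the trial. The contradiction rests on Sections 1.3 and 4.1, not on that sentence.
- A reader might infer that the rule costs about 25 DFS events (188.6 with no drop-out against 163.9, both at 34 months), or about 9 control deaths (59.9 against 51.2, using the control median OS of 54.4 months cited in Section 2.2.1). Those differences compare all planned drop-out with none. They include any true withdrawal of consent, which no wording change recovers. Recurrences count in DFS only on independent central radiology, so a note in the records yields deaths more readily than recurrences.
- A reader might infer unequal loss between arms from the longer treatment in one arm. The documents do not show it. Both arms have the same imaging schedule, and the control arm has added Week 35 and Week 48 follow-up.
- A reader might infer a power error. There is none: drop-out is in the calculation and the analysis is event-driven.
- Section 9.5.3 handles lost patients by name for OS, so the label alone does not fix the analysis.

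These limit the claim but do not remove the conflicting instructions. Section 9.5.3 says how to censor a lost patient; it does not tell the site whether to keep looking.

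**Conclusion.** The protocol gives sites two incompatible instructions for patients who cannot be reached and have not withdrawn consent. Following 7.3 and 8.2.4 could leave deaths unrecorded in DFS, RFS and OS, and so cause avoidable and possibly informative censoring. Neither the size nor the direction of any bias can be derived from the documents.

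The 57.5 of 300 is a ceiling on the patients this rule could touch before a DFS event. It holds only at the planned drop-out rate and under the exponential assumptions above. It does not count patients lost after a recurrence, who matter for OS. The 164 events, 300 patients and 90% power are unaffected. The point merits a wording change because the affected outcomes include the primary endpoint and the repair is cheap.

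**What to change.** - **Section 7.3:** replace the last sentence so that a patient who stays unreachable is recorded as lost to follow-up, not as withdrawn.
- **Section 8.2.4:** remove loss to follow-up as an end to survival ascertainment, in line with Sections 1.3 and 4.1.
- **Both sections:** state that at each survival time point and before every data cut-off the site checks medical records and, where law and consent allow, public death registers for vital status. Any scans found should go to central review, so that recurrences can count in DFS. For the individual patient, only explicit withdrawal of consent ends these checks.

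The cost is protocol and consent-form wording plus a small amount of site work before each cut-off. No sample-size or power figure changes. The change should be made prospectively, because the consent wording has to cover the searches.

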7.4 Replacement of permanently discontinued patients

Patients who are not considered evaluable for safety assessment during the dose escalation part of the trial may be replaced at the discretion of the sponsor.

Page 72 of 127 Version: 2.0 Date: 22 JAN 2024

In the Phase II part of the trial, patients who have been randomized but did not receive any treatment will be replaced.

8 TRIAL ASSESSMENTS AND PROCEDURES

The investigator (or an appropriate delegate at the investigator site) must obtain a signed and dated informed consent before performing any trial-specific procedures.

All screening evaluations must be completed and reviewed to confirm that potential trial patients meet all eligibility criteria. The investigator will maintain a screening log to record details of all patients screened and to confirm eligibility or record reasons for screening failure, as applicable.

Protocol waivers or exemptions would be protocol deviations.

See the SoA (Section 1.3) for all planned time points for assessments.

Any safety concerns should be discussed with the sponsor immediately upon occurrence or awareness to determine if the patient should continue or discontinue trial treatment.

Adherence to the trial design requirements, including those specified in the SoA, is essential and required for trial conduct, but there may be protocol deviations. Every effort should be made to ensure that protocol-required activities are completed as described. However, it is anticipated that from time to time there may be circumstances outside the control of the investigator that may make it unfeasible to perform the planned activity. In these cases, the investigator must take all steps necessary to ensure the safety and wellbeing of the patient. When a protocol-required activity cannot be performed, the investigator must document the reason for the missed activity and any corrective and preventive actions taken to ensure that required processes are adhered to as soon as possible. The sponsor must be informed of these incidents in a timely manner.

For samples being collected and shipped, detailed collection, processing, storage, and shipment instructions and contact information will be provided to the investigator site prior to initiation of the trial.

Procedures conducted as part of the patient's routine clinical management (e.g., blood count) and obtained before signing of the informed consent may be utilized for screening or baseline purposes provided the procedures met the protocol specified criteria and were performed within the time frame defined in the SoA (Section 1.3).

8.1 Screening/baseline assessments and procedures

At screening, the following demographic data will be recorded for all patients:

- Age
- Sex
- Ethnic group
- Race

Page 73 of 127 Version: 2.0 Date: 22 JAN 2024

Body weight, height, and derived body mass index

Adequate representation of demographic subgroups in this trial is necessary for understanding the safety and efficacy associated with novel cancer therapeutics. Medical history will be recorded for at the times given in the SoA (Section 1.3). It should include but not limited to lifetime history of cancer, tumor characteristics such as mutation status, cancer-related somatic genomic alterations and germline status, prior non-cancer significant medical conditions for the 2 years prior to trial entry, other clinically relevant diseases including tuberculosis, surgeries, use of alcohol and/or drugs abuse and reproductive status.

8.2 Efficacy assessments

Planned time points for efficacy assessments are provided in the SoA (Section 1.3). Response assessments will follow the procedures outlined in RECIST 1.1.

8.2.1 Tumor evaluations (CT/MRI)

Screening assessments must include computed tomography (CT) scans (with i.v. contrast unless contraindicated) of the chest and abdomen and pelvis. Magnetic resonance imaging (MRI) of the abdomen and pelvis may be used in patients for whom CT scans with contrast are contraindicated (i.e., patients with contrast allergy or impaired renal clearance). CT of the chest without contrast may be performed for patients for whom CT scans with contrast are contraindicated.

Patients should be evaluated with the same method of assessment and the same technique (CT or MRI) used at baseline screening, throughout the trial. At the investigator's discretion, imaging may be repeated at any time if disease recurrence or a new primary cancer is suspected.

On trial, imaging assessments will be performed on the following schedule: from C1D1 every 3 months (12 weeks) for 2 years, and then every 6 months for 3 years thereafter (±7 days).

Tumor assessments will be submitted for central review and assessed by radiologists blinded to the treatment assignment. The baseline screening assessments must be obtained post-operatively and must not be more than 4 weeks prior to first trial treatments. The baseline screening assessments must be available to confirm NED prior to enrollment of patients into both phases of this trial.

8.2.2 Tumor marker CA19-9

CA19-9 measurements will be taken to follow disease according to the SoA (Section 1.3).

8.2.3 Eastern Cooperative Oncology Group performance status

The ECOG PS should be assessed by the investigator or suitably qualified designee according to Table 14.

Page 74 of 127 Version: 2.0 Date: 22 JAN 2024

Table 14: Eastern Cooperative Oncology Group performance status grading

Grade	Description
0	Fully active, able to carry on all pre-disease performance without restriction
1	Restricted in physically strenuous activity, but ambulatory and able to carry out work of a light or sedentary nature, e.g., light housework, office work
2	Ambulatory and capable of all self-care, but unable to carry out any work activities, up and about more than 50% of waking hours
3	Capable of only limited self-care, confined to bed or chair more than 50% of waking hours
4	Completely disabled. Cannot carry on any self-care. Totally confined to bed or chair
5	Dead

